#### 1.1 Study design

This study is a phase IIb, multicenter, multi-national, double-blind, randomized, parallel-arm, placebo-controlled study to evaluate the effect of 5 dose levels of CSJ117 in adult subjects with inadequately controlled asthma despite medium to high dose ICS plus LABA.

The study will include:

- A screening period of approximately 2 weeks
- A single blinded placebo run-in period of 4 weeks (must be extended to 8 weeks for patients experiencing an asthma exacerbation or respiratory tract infection during the run-in period)
- A double blinded treatment period of 12 weeks
- A follow-up period of 12 weeks, study drug free, following the last dose of study drug. Or a follow-up period of 8 weeks for patients that discontinued the study due to early termination.

	Screening	Run-in			Treatment				Follow-up				
	30 3	•			- Fluticasone/Salmeterol 250/50 b.i.d OR 500/50 b.i.d**								
		Placebo Once daily			Placebo once daily CSJ117 0.5 mg once daily				Discontinuation of CSJ117				
					CS I11 / 1 mg once daily								
					CSJ117	2 mg once dai	ily						
				CSJ117 4 mg once daily									
					CSJ117	8 mg once dai	ily						
	2 weeks		4 weeks*				12 weeks				12 w	eeks	
Visit	Screening	Run-In	Phone Visit	End of Run-In	Day 1	Week 2	Week 4	Week 8	Week 12	Week 14	Week 16	Week 20	Week 24
Day	-42	-28	-14	1	1	15	29	57	85	99	113	141	169

Figure 1-1 Study design

or patients experiencing an asthma exacerbation during the run in perioc

\*\*depending on ICS-LABA entry dose

For business use only

At randomization, subjects will be stratified by their geographic region and blood eosinophil count (EOS) ( $\geq$  300 or < 300 cells/µl), measured at the screening visit. Approximately 52% of the total study population will be enrolled in the high EOS stratum. If recruitment for one EOS stratum is completed, only patients with baseline EOS count allowing randomization to the other stratum will be eligible. Subjects will be randomized in a 2:1:1:1:2:2 ratio to receive placebo or one of 5 doses of CSJ117 (0.5, 1, 2, 4, 8 mg) once daily for 12 weeks. All arms will have the same stratification ratio.

A Safety Extension Study of CSJ117 is planned (CSJ117A12201E1). Patients who successfully complete 12 weeks of treatment or 12 weeks of follow-up in this study (Study CCSJ117A12201C) may be offered participation in the Safety Extension Study; patient participation in the Safety Extension Study will be optional. Patients not entering the safety extension study directly after the treatment period will complete the 12 week follow-up period.

Originally, approximately 625 patients were to be randomized into this study. Subsequent deprioritzation of the program has led to early termination of this study, resulting in actual enrollment of 335 patients. Detailed information regarding sample size calculation is provided in Section 3.

The primary endpoint will be assessed at the end of the treatment period.

Interim analyses (IA) on safety data are planned for an independent external safety data monitoring committee (DMC) to evaluate the safety data. DMC meetings will occur approximately twice a year. Detailed information regarding DMC analysis will be provided in the DMC charter and a separate DMC SAP.

One or more interim analyses may be conducted to support decision-making in relation to the current clinical study, or the future of the sponsor's clinical development plan or in case of any safety concerns from this study or ongoing clinical studies.

#### 1.2 Study objectives and endpoints

Section 2 of the study protocol lists the following primary, secondary, objectives. All immunogenicity analysis and PK analysis will be conducted and reported separately other than in the CSR.

Table 1-1 Objectives and related e	ndpoints			
Objective(s)	Endpoint(s)			
Primary objective(s)	Endpoint(s) for primary objective(s)			

 
To characterize the dose-response relationship of five doses of CSJ117 inhaled daily on lung function, compared with placebo, at the end of the 12-week active-treatment period.
 
	
 
Average change from baseline in pre-dose FEV1 (L) at Week 8 and Week 12.
 
			
Secondary objective(s)	Endpoint(s) for secondary objective(s)			

 
To characterize the dose-response relationship of five doses of CSJ117
 
	
 
Average change from baseline in FeNO at Week 8 and Week 12.
 
			

Objective(s)	Endpoint(s)
inhaled daily on FeNO compared with placebo, during the 12-week active- treatment period	

 
To assess immunogenicity of five doses of CSJ117 during the study
 
	
 
Measurement of Anti-Drug Antibodies (ADA) titers at baseline and during the study (Week 0 [Day 1] to Week 24)
 

 
To characterize the systemic pharmacokinetic (PK) profile of multiple inhaled daily doses of CSJ117 during the 12 week, active treatment period and the 12 week, follow-up period
 
	
 
Measurement of total CSJ117 serum concentration during the study (Week 0 [Day 1] to Week 24) and calculation of PK parameters (e.g., Ctrough, Racc, T/2).
 

• To characterize the efficacy of five doses of CSJ117 once daily, compared with placebo, on peak expiratory flow (PEF; AM and PM), as assessed by mean morning and mean evening PEF over the 12-week active-treatment period	
 
Change from baseline in peak expiratory flow (PEF; am and pm), as assessed by mean morning and mean evening PEF in each week (average over 7 days) during 12 weeks of treatment.
 

• To characterize the efficacy of five doses of CSJ117 once daily, compared with placebo, on ACQ-5 over the 12-week active-treatment period.	
 
Average change from baseline in ACQ-5 score at Week 8 and Week 12.
 

• To characterize the efficacy of five doses of CSJ117 once daily, compared with placebo, on change from baseline in Asthma Quality of Life Questionnaire (AQLQ) score at the end of the 12-week active-treatment period	
 
Average change from baseline in AQLQ+12 score at Week 8 and Week 12
 

• To characterize the efficacy of five doses of CSJ117 once daily, compared with placebo, on daytime and nighttime asthma symptoms over the 12-week active- treatment period	
 
Average change from baseline in ADSD and ANSD score at Week 8 and Week 12.
 

 
To characterize the efficacy of five doses of CSJ117 once daily, compared with placebo, on daily short-acting β-agonist (SABA) use over the 12-week active- treatment period
 
	
 
Change from baseline in number of puffs of SABA taken per day in each week (average over 7 days) during 12 weeks active-treatment period
 

• To assess the safety of five doses of CSJ117 once daily, compared with placebo, with respect to adverse events (AE), electrocardiograms (ECGs), vital signs and laboratory tests	• Summaries of treatment-emergent adverse events, systolic and diastolic blood pressure, pulse rate, body weight, ventricular rate, RR interval, PR interval, QRS duration, heart rate, and Fridericia's QTc, laboratory values and change from baseline for continuous laboratory values.

### 2 Statistical methods

#### 2.1 Data analysis general information

The statistical analysis will be performed by Novartis. The most recent version of SAS® (SAS Institute Inc., Cary, NC, USA) available in the statistical programming environment of Novartis will be used for the analysis. R version 3.6.1 may also be used as appropriate.

#### 2.1.1 General definitions

The terms 'double-blind treatment' will be used in this document and refer to the double-blind CSJ117 doses and placebo.

#### 2.1.1.1 Study day

Study day will be defined as the number of days since the date of first dose of double-blind treatment. The date of first dose of double-blind treatment will be defined as Day 1 and the day prior to first dose of double-blind treatment will be defined as Day -1.

Therefore, for a particular date, study day will be calculated as follows:

for dates on or after the date of first dose of double-blind treatment,

Study day = Assessment date - Day 1 + 1;

for dates prior to the date of first dose of double-blind treatment,

```
Study day = Assessment date - Day 1.
```

If a patient never received any double-blind treatment, the date of randomization will be used as Day 1.

#### 2.1.1.2 Baseline definition

In general, baseline is defined as the last measurement taken before the first dose of doubleblind treatment. Details on calculation of baseline will be provided in the latter sections.

For patients who never received any double-blind treatment, the baseline is the last measurement taken before randomization.

#### 2.1.1.3 Post-baseline definition

All data collected after the start of double-blind treatment are defined as post-baseline. For patients who are not treated, the post-baseline is any assessments after randomization.

When change from baseline is of interest the following formula will be used for each scheduled visit and time-point where baseline and post-baseline values are both available:

Change from baseline = post-baseline value – baseline value.

If not stated otherwise for efficacy analyses, on-treatment values are defined as values taken post-baseline but no later than 1 day after last dose of double-blind treatment. Off-treatment values are defined as post-baseline values taken more than 1 day after last dose of double-blind treatment.

Details on calculation of post-baseline values are provided in the latter sections.

#### 2.2 Analysis sets

The Randomized Analysis Set (RAS) consists of all randomized subjects. Subjects will be analyzed according to the treatment they were assigned to at randomization. Demographics and baseline characteristics will be summarized using the RAS.

The Full Analysis Set (FAS) comprises all subjects to whom double-blind treatment has been assigned and who received at least one dose of double-blind treatment. Subjects will be analyzed according to the treatment they have been assigned to during the randomization procedure. The FAS will be used for the analysis of all efficacy variables.

The Safety Set includes all subjects who received at least one dose of double-blind treatment. Subjects will be analyzed according to the treatment they received, where treatment received is defined as the randomized/assigned treatment if the participant took at least one dose of that treatment or the first treatment received if the randomized/assigned treatment was never received. The Safety Set will be used for the analysis of all safety variables.

The PK set will include all patients with at least one evaluable drug concentration data sample.

#### 2.2.1 Subgroup of interest

Subgroup analyses are conducted to assess consistency of the treatment effect among the subgroups, without multiplicity adjustments. The following subgroups will be evaluated for the primary endpoint:

- Age group  $(18 < 40, 40 < 65, \ge 65 \text{ years})$
- Gender (male, female)
- Race (White, Asian, Black, other)

- Region
- Body mass index (BMI) ( $\leq 30.0 \text{ kg/m}^2$ ,  $> 30.0 \text{ kg/m}^2$ )
- Duration of asthma (1 5 years, > 5 10 years, > 10 15 years, > 15 20 years, > 20 years)
- Pre-bronchodilator FEV1 in % of predicted FEV1 (<40%, 40 < 50%, 50 < 60%, 60% < 80%, 80 85%)

- Use of medications at screening in addition to ICS/LABA controllers (Yes, No)
- Prior asthma treatment (medium or high ICS/LABA)
- Atopic asthma status (Yes, No)
- Baseline FeNO (< 25 ppb,  $\geq$  25 ppb)
- Number of exacerbations in the prior year  $(1, 2, \ge 3)$
- Baseline ACQ-5 (<1.5, 1.5 <2, 2 <2.5,  $\ge 2.5$ )

# 2.3 Patient disposition, demographics and other baseline characteristics

No inferential testing on the differences in patient disposition, demographics and other baseline characteristics between treatment arms will be performed.

#### 2.3.1 Patient disposition

The RAS will be used for the summary and listing of patient disposition. The screening disposition and the analysis sets table will be based on all screened patients.

The number of patients in the RAS will be summarized by region, country, center and treatment group. Further, the overall number of patients who entered completed, and discontinued study will be summarized including the reasons for discontinuation for each period: pre-randomization, double-blind treatment and follow-up.

Number of patients with protocol deviations (PDs) and with Covid-19 related PDs will be tabulated by category (e.g., selection criteria not met, subject not withdrawn as per protocol, treatment deviation, prohibited concomitant medication, other) and deviation.

COVID-19 pandemic-related impact to protocol adherence captured as protocol deviations will be tabulated by Pandemic-related PD Relationship to COVID-19 by treatment and category.

The number of patients included in each analysis set will be tabulated. Patients exclusion from analysis sets will be listed for all patients with reasons for exclusion (i.e. including both protocol and non-protocol deviations).

#### 2.3.2 Patient demographics and other baseline characteristics

Demographics and other baseline characteristics will be summarized and listed using the RAS.

Demographic characteristics, including age, gender, race, ethnicity, region, height, weight, and BMI will be summarized by treatment and overall.

Novartis SAP

Baseline disease characteristics, including duration of asthma, run-in spirometry (FEV1, FVC, FEV1/FVC and % of predicted FEV1 pre- and post-bronchodilator, FEV1 reversibility), asthma exacerbation history, smoking history, atopic asthma status (Yes/No), baseline ACQ-5, baseline AQLQ+12, blood eosinophils at screening, prior asthma treatment (medium/high ICS/LABA) will be summarized.

Summaries of continuous variables will include mean, standard deviation (SD), first and third quartile, median, minimum and maximum. Summaries of categorical variables will show absolute (n) and relative (%) frequencies including a category for missing data if any.

No statistical analyses will be provided for baseline comparability among the treatment groups.

In addition, the following categorizations of continuous variables will be done:

- Age into 18 < 40, 40 < 65, and  $\ge 65$  years;
- BMI into  $\leq 30.0 \text{ kg/m2}$  and > 30.0 kg/m2;
- Duration of asthma into < 1 year, 1 5 years, > 5 10 years, > 10 15 years, > 15 20 years, and > 20 years;
- Severity of airflow limitation: pre-bronchodilator FEV1 % predicted values into 40 < 50%, 50 < 60%, 60% < 80%, and 80 85%

- ACQ-5 into  $1.5 < 2, 2 < 2.5, and \ge 2.5$

#### 2.3.3 Medical history/current medical condition

Medical history will be coded with the Medical Dictionary for Regulatory Activities terminology (MedDRA) using the most recent version at the time of database lock. Relevant medical histories and current medical conditions, including pre-specified protocol solicited events, will be summarized for the RAS by primary system organ class and preferred term by treatment group.

# 2.4 Treatments (study treatment, rescue medication, concomitant therapies, compliance)

All summaries of treatments will be performed on the Safety Set.

#### 2.4.1 Study treatment / compliance

The duration of exposure in days to each treatment group (CSJ117 doses or placebo) will be summarized by means of descriptive statistics. In addition, the duration of exposure will be summarized as a categorical variable classified into  $\leq 2$  weeks,  $\geq 2 - 4$  weeks,  $\geq 4 - 6$  weeks,  $\geq 6 - 8$  weeks,  $\geq 8 - 10$  weeks,  $\geq 10 - 12$  weeks,  $\geq 12 - 13$  weeks, and  $\geq 13$  weeks.

Duration of exposure to double-blind treatment will be calculated as the number of days between the first dose date and the last dose date exposed to that treatment over the specified period (expressed as: Duration of exposure = Date of last known dose of double-blind treatment - Date of first dose of double-blind treatment + 1).

The number of patients who permanently discontinued from double-blind treatment and the reasons will be summarized by treatment group. Patients who permanently discontinued from double-blind treatment will be listed including reason and date of discontinuation.

For business use only

Compliance will be calculated as the percentage of the number of days where double-blind treatment was administered as per protocol divided by the duration of exposure (i.e., the number of days between first and last dose).

Compliance will be categorized by < 80 % and 80 % - 100 % and summarized by treatment group.

#### 2.4.2 **Prior**, concomitant and post therapies

Summaries for asthma-related medications will be performed separately for medications prior to the start of double-blind treatment (medications starting prior to Day 1) and for concomitant medications (medications which were taken anytime between the first dose and last dose of double-blind treatment, inclusive). Medications can be considered both prior and concomitant. Asthma-related medications will be summarized by pre-specified drug categories, route of administration, preferred term, and treatment group.

Non-asthma related medication prior to and after the start of double-blind treatment will be summarized by the Anatomical Therapeutic Chemical (ATC) classification system, preferred term, and treatment group. More than one ATC class per medication is possible and the medication will be reported under all applicable classes.

Surgical and medical procedures (non-drug therapies) are coded using MedDRA. Presentations will be done by MedDRA primary system organ class and preferred term, separately for prior and concomitant procedures.

#### 2.5 Analysis of the primary objective

The primary objective of this study is to characterize the DR (dose response) efficacy relationship among CSJ117 doses (0.5, 1, 2, 4, and 8 mg daily) and placebo with regards to the average change from baseline in pre-dose  $FEV_1$  (L) at Week 8 and Week 12. The goals associated with this objective are below.

- To confirm an overall drug response signal
- To estimate the dose(s) that corresponds to the target effect over placebo based on the estimated DR curve

#### 2.5.1 **Primary endpoint**

The primary estimand, defined below, quantifies a hypothetical on-treatment effect during stable periods (i.e. outside of periods of acute disease worsening requiring additional asthma medications). This estimand targets the maximum treatment effect for CSJ117 and allows selection of the best dose for those who take it for 12 weeks.

- **Population**: adult patients with inadequately controlled asthma on medium or high dose ICS/LABA, alone or with up to two additional asthma controllers (LTRA, LAMA or theophylline)
- Variable: Average change from baseline in pre-dose FEV1 after 8 and 12 weeks of treatment
- **Treatment**: CSJ117 or placebo

- Intervention effect of interest: Effect of interventions initiated at randomization during stable periods and that would have been observed had all patients remained on their assigned treatment for 12 weeks, with the following post-randomization events accounted for by assessing:
  - Intake of non-study drug with effect on FEV1: the effect outside of periods of worsening disease that necessitate such non-study drug
  - Discontinuation of study treatment due to any reason: hypothetical value of the average between Week 8 and Week 12 pre-dose FEV1 had the patients not stopped the study treatment
  - The case where patient received treatment different from the assigned treatment: hypothetical value of the average between Week 8 and Week 12 pre-dose FEV1 had the patient remained on the assigned treatment for 12 weeks
- Summary measure: mean difference between CSJ117 and placebo

This estimand is considered appropriate for a dose finding trial in order to obtain a clear dose response signal and understand the maximum potential effect of the drug.

The baseline value is defined as the average of the values taken approximately 2 hours 45 minutes and 2 hours 15 minutes prior to the first dose of double-blind treatment at Day 1. If one of the two values is missing (or is not confirmed to be pre-dose) then the remaining non-missing value will be taken as the baseline. If both values are missing (or are not confirmed to be pre-dose), then the measurements taken at the run-in visit will be used as the baseline.

#### 2.5.2 Statistical hypothesis, model, and method of analysis

The Multiple Comparison Procedure – Modelling (MCP-Mod) methodology (see Bretz et al 2005 and Pinheiro et al 2014) will be employed to assess the primary objective. An overview of the steps for the MCP-Mod methodology is given below.

#### Step 1 (Testing an overall dose-response signal - MCP part):

The covariate adjusted least-squares means averaged across Week 8 and Week 12 visits for each individual dose group and the corresponding variance-covariance matrix will be obtained from a linear mixed effects model for repeated measures (MMRM) with terms for baseline FEV1, visit, treatment, randomization strata – eosinophil count (EOS) ( $\geq$  300 or < 300 cells/µl) and region, treatment-by-visit interaction, and baseline FEV1-by-visit interaction, FEV1 prior to inhalation, and FEV1 within 30 min post inhalation of salbutamol/albuterol (components of reversibility test results at the run-in visit) as fixed effects. To allow adjustment for correlations between time points within patients, an unstructured variance-covariance structure will be used.

The adjusted treatment means from the MMRM will be used to test the null hypothesis of a flat DR relationship for the primary efficacy endpoint at a two-sided significance level of 5% against the alternative hypothesis of a non-constant DR curve. Two one-sided tests will be performed to obtain the two-sided test. The testing will be performed with a multiple contrast test described in the MCP-Mod methodology.

A wide range of possible dose response relationship will be considered to take model uncertainty into account

**Step 2** (Estimation of the dose-response curve and target dose – Mod part):

Once the DR signal is tested, the DR curve and the target dose(s) of interest will be estimated by model averaging. A large number of bootstrap samples from the multivariate normal distribution will be drawn with adjusted means from the MMRM and corresponding covariance matrix. For each sample:

- DR models from the candidate families will be fitted to the data and the best model according to the generalized Akaike information criterion will be chosen.
- The predictions for dose response will be obtained from the best model.

The final DR curve estimate is the median of these predictions while confidence intervals will be calculated from the quantiles. The final DR curve estimate with the model-based two-sided

For business use only

95% confidence interval will be presented graphically. In addition, the plot will include the mean responses from the MMRM and the associated 95% confidence intervals for each of the studied dose groups. This bootstrap model averaging approach reflects model uncertainty in the inference and typically leads to more reliable confidence intervals as well as more precise estimates of the dose-response curve compared to selection of a single model (Bornkamp 2015; Schorning et al 2016).

#### 2.5.3 Handling of missing values/censoring/discontinuations

Despite all attempts to ensure complete follow-up for all patients, some patients may not be followed for pre-dose  $FEV_1$  for the whole planned study duration.

The FEV1 value analyzed at each post-baseline visit is based on the average of the two FEV1 assessments taken at approximately 45 minutes and approximately 15 minutes prior to the dosing of study drug at clinic visits. Since the estimand is related to an effect outside of periods of acute disease worsening requiring additional asthma medications, spirometry measurements taken within 6 hours of rescue medication, 7 days of intake of systemic corticosteroid use, 3 months of a single depot corticosteroid injection, 24 hours of background medication use, and/or 48 hours of LAMA use will be set to missing. In cases where one of the two values is missing, the remaining non-missing value will be taken as pre-dose FEV1. If both values are missing, then their pre-dose FEV1 will be regarded as missing at that visit.

For the primary analysis, only on-treatment data (from date of first dose of double-blind treatment up to 1 day after date of last dose) will be used as the estimand specifies a hypothetical on-treatment effect. Missing on-treatment data will not be explicitly imputed as the MMRM implicitly imputes missing data assuming the missing at random (MAR) mechanism.

The imputation procedures related to the pre-dose  $FEV_1$  supportive analyses (Section 2.5.4) are "jump-to-reference" (J2R) and MAR (Carpenter et al 2013). The imputations will be based on all available data (i.e. from all scheduled timepoints) using all covariates as specified in the MMRM. For J2R, only placebo (reference) data will be used. For MAR, data from the same treatment arm will be used for building the imputation model. Imputation of intermittent missing observations before treatment discontinuation will be carried out following a MAR mechanism for all treatment arms. Additional details are provided in Section 5.5.

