The treatment of asthma exacerbations including the initiation of systemic corticosteroids should be done according to investigator's or treating physician's medical judgement and should be in line with their institutional, national and international recommendations. If systemic corticosteroids are required, a patient may return to the study assessments after successfully completing an Oral Corticosteroid (OCS) taper. If patients require treatment with systemic steroids longer than 3 weeks, including taper, or chronic systemic steroid administration, they must be discontinued from treatment.

If indicated for the treatment of an adverse event, including asthma exacerbation, any treatment (including medications in Table 6-3) deemed necessary by treating physician for the safety of the patient is allowed from the start of the event until the event is resolved. If it is transitioning to chronic treatment, the investigator should discuss with Novartis Medical Monitor. Patients may NOT self-medicate (other than administration of rescue medication) or adjust therapy without permission/guidance from treating physician.

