6.2.2 Prohibited medication

The specified minimum washout periods prior to the run-in are described in Table 6-3. Use of the treatments displayed in Table 6-3 is NOT allowed after the beginning of run-in (unless for the treatment of adverse events and asthma exacerbations). Each concomitant drug must be individually assessed against all exclusion criteria and the tables below to see if it is allowed. If in doubt, the investigator must contact the Novartis medical monitor or designee before randomizing a patient or allowing a new medication to be started. Medications must be assessed for adherence to the indication and other inclusion/exclusion criteria.

Class of medication	Minimum cessation prior to Run-In ^{1,2}
Other investigational drugs	30 days or 5 half-lives, whichever is longer
Live attenuated vaccine*	2 days
Inactivated influenza vaccination, pneumococcal vaccination or any other inactivated vaccine*	2 days
Short-acting anticholinergics (SAMA)	6 hours
Long acting muscarinic antagonists (LAMAs)*	7 days
Fixed combinations of short-acting β_2 agonists and short-acting anticholinergics (SABA/SAMA)	12 hours
Xanthines*	7 days
Leucotriene Receptor Antagonists (LTRAs) and leucotriene synthesis inhibitors*	7 days
Systemic mast cell stabilizers (e.g., cromoglycate, nedocromil, ketotifen)*	7 days
Oral corticosteroids	6 weeks
Short-acting, intra-articular, intramuscular, intravenous corticosteroid	6 weeks
Long acting, intra-articular, intramuscular depot corticosteroids	3 months and 2 weeks
Monoclonal antibodies for the treatment of asthma (e.g. omalizumab, mepolizumab, benralizumab etc.) (investigational or approved)	5 half-lives or 6 months, whatever is longer
Other anti-TSLP drugs (investigational or approved)	Not permitted
Methotrexate, gold salts, cyclosporine, troleandomycin, azathioprine, other immunomodulator drugs or immunomodulatory monoclonal antibodies	6 months

Table 6-3Prohibited medication

¹ This table is not considered all-inclusive. Medications should be assessed for adherence to the indication and other inclusion/exclusion criteria

² These medications are also prohibited if administered for other indications

*these medications can be used again in the follow up period

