12.4.3 Handling of missing values/censoring/discontinuations

Despite all attempts to ensure complete follow-up for all patients, some patients may not be followed for pre-dose FEV1 for the whole planned study duration.

The FEV1 value analyzed at each post-baseline visit is based on the average of the two FEV1 assessments taken at approximately 45 minutes and approximately 15 minutes prior to the dosing of study drug at clinic visits. Since the estimand is related to an effect outside of rescue med intake, spirometry measurements within 6 hours of rescue medication, within 7 days of intake of systemic corticosteroid use, or within 3 months of a single depot corticosteroid injection, or within 24 hours of background medication use, or within 48 hours of LAMA use will be set to missing. In cases where one of the two values is missing, the remaining non-missing value will be taken as pre-dose FEV1. If both values are missing, then their pre-dose FEV1 will be regarded as missing at that visit.

For the primary analysis, only on-treatment data (from date of first randomized dose up to 1 day after date of last randomized dose) will be used as the estimand specifies a hypothetical on-treatment effect. Missing on-treatment data will not be explicitly imputed as the MMRM implicitly imputes missing data assuming the missing at random (MAR) mechanism.

The imputation procedures related to the pre-dose FEV1 supportive analyses (Section 12.4.4) are "jump-to-reference" (J2R) and MAR (Carpenter et al 2013). The imputations will be based on all available data (i.e. from all scheduled timepoints) using all covariates as specified in the MMRM. For J2R, only placebo (reference) data will be used. For MAR, data from the same treatment arm will be used for building the imputation model. Imputation of intermittent missing observations before treatment discontinuation will be carried out following a MAR mechanism for all treatment arms. Additional details will be available in the SAP.

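### The list of drugs that set FEV1 to missing is narrower than the estimand: leukotriene drugs, xanthines, mast-cell stabilisers, short-acting anticholinergics and biologics have no rule

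*SAP*

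**What the plan says.** The primary estimand (SAP 2.5.1) treats intake of a non-study drug with an effect on FEV1 by targeting "the effect outside of periods of worsening disease that necessitate such non-study drug". It does not restrict the drug class. SAP 2.5.4, item (a), repeats this for the supplementary analysis.

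SAP 2.5.3 implements it with a closed list. Set to missing are "spirometry measurements taken within 6 hours of rescue medication, 7 days of intake of systemic corticosteroid use", and values within 3 months of a single depot steroid injection, 24 hours of background medication or 48 hours of LAMA. Protocol 12.4.3 has the same list with a narrower reason: "Since the estimand is related to an effect outside of rescue med intake". The SAP widened the reason to acute worsening that needs additional asthma medication, but left the drugs unchanged. Protocol 6.1.2.1 equates rescue medication with SABA.

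Protocol 6.2.1.1 says that, when indicated for an adverse event including an exacerbation, "any treatment (including medications in Table 6-3) deemed necessary by treating physician for the safety of the patient is allowed" until the event resolves. Protocol 6.2.2 lifts its ban in the same way: "unless for the treatment of adverse events and asthma exacerbations". Table 6-3 includes "Leucotriene Receptor Antagonists (LTRAs) and leucotriene synthesis inhibitors", xanthines, systemic mast-cell stabilisers, SAMA, fixed SABA/SAMA combinations and "Monoclonal antibodies for the treatment of asthma".

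**The concern.** If the list is programmed as written, some FEV1 values that the estimand sets aside will enter the primary model. LAMA shows that the sponsor expected some on-treatment use of Table 6-3 controllers, since LAMA is itself in that table and has a data rule. The protocol groups LAMA with LTRA and theophylline in the estimand population and in inclusion criterion 4, yet only LAMA has a window, and no reason is given.

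Add-on controllers are plausibly started more often where study treatment works least. Values raised by them would then lift placebo and low-dose means, shrink the difference from placebo and flatten the dose-response curve that the trial is meant to characterise.

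**Working it through.** **Step 1. The classes side by side.** Cessation times are from Table 6-3 and data windows from SAP 2.5.3.

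| Class | Table 6-3 time | FEV1 window | Within the 7-day steroid window if stopped with a steroid-treated exacerbation? |
|---|---|---|---|
| LTRA / leukotriene synthesis inhibitors | 7 days | none | yes, equal |
| Xanthines | 7 days | none | yes, equal |
| Systemic mast-cell stabilisers | 7 days | none | yes, equal |
| SAMA | 6 hours | none | yes |
| SABA/SAMA | 12 hours | at most 6 hours, through the SABA part | yes |
| Asthma monoclonal antibodies | 5 half-lives or 6 months | none | no |
| LAMA (for comparison) | 7 days | 48 hours | has its own rule |

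**Step 2. Routes already closed in the primary analysis.**
- Protocol 8.6.4 defines a non-fatal exacerbation by at least 3 days of systemic corticosteroid or a depot dose, defers scheduled spirometry until full resolution, and dates the end of the event by the last steroid day. A drug stopped with the event is followed by the 7-day steroid exclusion.
- Protocol 9.1.1 requires study treatment to stop on permanent use of a prohibited drug. SAP 2.5.3 uses data only up to 1 day after the last dose.
- Protocol 4.1.1 forbids other changes to background therapy during treatment.

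**Step 3. What remains.**
- Worsening or another adverse event treated without systemic steroids triggers neither the steroid window nor the exacerbation deferral. Protocol 8.4.3.4 expects early intervention on eDiary alerts.
- For treatment turning chronic, protocol 6.2.1.1 asks only for a discussion with the medical monitor. Until use is called permanent, values remain on-treatment.
- Six months exceeds the 12-week treatment period, so one antibody dose could affect every later visit.
- In the supplementary analysis, patients who stop treatment stay in the study (protocol 6.1.4). Item (b) of SAP 2.5.4 uses their actual off-treatment values, and nothing visible applies item (a) to these classes.

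**Step 4. The plan's own figures.** Inputs from SAP section 3: variances 0.1461 and 0.1456, covariance 0.1163, maximum effect 0.120 L, one-sided 2.5%, allocation 2:1:1:1:2:2. The nine candidate shapes are in protocol 12.4.2.
- SD = √[(0.1461 + 0.1456 + 2 × 0.1163)/4] = √0.131075 = 0.3620 L (stated 0.3622).
- 531/0.85 = 624.7, so 625.
- Simulating the maximum-contrast test (1,000,000 draws, critical value 2.313) gives 81.6% average power at 531, in line with the stated figure of above 80%.

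The gap does not touch this calculation. It concerns which values enter the model.

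**Step 5. Size if the values stay in.** Bias in the CSJ117 minus placebo difference = (share using on CSJ117 − share using on placebo) × drug effect on FEV1. Both inputs are assumptions.
- 2 points more use on placebo, 50 mL: −0.02 × 50 = −1 mL.
- 8 points more, 150 mL: −0.08 × 150 = −12 mL, and 12/120 = 10%.
- A wider range of 1 to 10 points and 50 to 200 mL gives 0.5 to 20 mL.

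This takes both Week 8 and Week 12 as affected; if only one is, the figure halves. Shrinking the maximum effect accordingly, average power at 531 goes from 81.6% to 80.9% (1 mL), 78.2% (5 mL), 74.5% (10 mL) and 66.3% (20 mL).

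**Step 6. Cost of setting the values to missing.** If a further 1, 2 or 5% of 625 patients contribute nothing beyond the planned 15%, average power is 81.1, 80.7 or 79.2%. With the 335 actually enrolled (SAP 1.1) and 15% missing, power is 55.1%, falling to 54.6, 54.1 or 52.6%.

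**The case against.** The best defence is that the protocol's other rules do most of the work, and Step 2 shows that this largely stands. Two stronger readings are tempting, and the documents do not support them. A reader might infer that patients can be switched to another controller and still count in the primary analysis. A permanent switch requires stopping study treatment, after which their values drop out. A reader might also infer that the added drugs' benefit is credited to CSJ117. The values stay in the assigned arm, placebo included, and would inflate the effect only if use were higher on CSJ117.

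Further points have weight. An LTRA or theophylline started at Week 6 must run for about six weeks to affect both endpoint visits, which is close to chronic use. No other at-home rescue is permitted (protocol 6.1.2.1), and biologics may not be added even in follow-up (protocol 4.1.1), so both may be rare. Even 12 mL is small beside the planned 76.93 mL half-length of the 95% interval for the placebo-adjusted curve. Table 6-3 gives pre-run-in cessation times that the plan does not otherwise use as data windows: LAMA has 7 days there and 48 hours in SAP 2.5.3. For the supplementary analysis, dropping values under later controllers could conflict with item (b). SAP 2.5.4 refers to section 5.5 for details, and the text available there shows only the primary model.

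These points limit the size and leave room in the choice of windows. They do not supply a rule for the classes that have none.

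**Conclusion.** The mismatch stands: the rule that implements the primary estimand covers fewer drugs than the estimand does. In the primary analysis it is confined to the three routes in Step 3. In the supplementary analysis it concerns off-treatment values, subject to any detail of section 5.5 that is not visible.

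If use is higher on placebo or low doses, the bias is towards no effect and a flatter curve, by about 1 to 12 mL of 120 mL under the assumed 2 to 8 points and 50 to 150 mL. The direction and size both rest on assumption, because the documents give neither usage rates nor drug effects. The true effect may be close to zero. The correction is still worth making, because it concerns the primary endpoint and costs little.

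**What to change.** Before unblinding, extend the set-to-missing list in SAP 2.5.3 to the omitted classes. The windows would be data-handling rules only, with no change to what patients may receive. One ready source is Table 6-3:
- 7 days for leukotriene drugs, xanthines and systemic mast-cell stabilisers;
- 6 hours for SAMA and 12 hours for SABA/SAMA;
- 5 half-lives or 6 months for asthma antibodies, in effect all later visits.

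In SAP 2.5.4, state how item (a) applies to off-treatment values under these drugs and how it fits with item (b). Report a sensitivity analysis with the present list. If the sponsor prefers to leave a class out, the SAP should say why.

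The cost is SAP wording and programming from concomitant-medication data already collected at every visit. A few more values would be missing and handled under MAR, in patients who were worsening; Step 6 gives the loss of power. The new 7-day windows would also sit beside a 48-hour LAMA window, and the SAP should acknowledge that difference.
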